11. VIROLOGY

The virology analyses will be mainly for the CVF populations using genotype and phenotype data based on plasma sample, unless otherwise specified.

Table 8 provides an overview of the planned analyses, with further details of data displays being presented in Appendix 13: List of Data Displays.

Table 8 Overview of Planned Virology Analyses

Endpoint	Absolute			
	Summary		Individual	
	T	F	F	L
Genotypic resistance at time of CVF^[1]				
Prevalence of genotype	Y ^[2]			
On Treatment mutation	Y ^[2]			
Phenotypic resistance at time of CVF^[1]				
Prevalence of phenotype	Y ^[3]			
Fold change for CAB and RPV	Y			
IN, PR/RT replication capacity				Y
Other				
Genotypic and phenotypic data on the last on-treatment isolates in subjects with HIV-1 RNA ≥ 200 c/mL	Y			

NOTES:

- T = Table, F = Figure, L = Listing, Y = Yes display generated.
 - Stats Analysis = Represents TFL related to any formal statistical analyses (i.e. modelling) conducted.
 - Summary = Represents TFL related to any summaries (i.e. descriptive statistics) of the observed raw data.
 - Individual = Represents FL related to any displays of individual subject observed raw data.
1. For the CVF as indicated by two consecutive plasma HIV-1 RNA levels ≥ 200 c/mL after prior suppression to < 200 c/mL, the first visit of these two consecutive visits is defined as 'the suspected visit', and the 2nd one is the confirmed visit. Sample used for resistance testing is taken at the suspected visit date, and only tested once a subject confirms virological failure at a subsequent visit. If the test fails with the sample at the suspected visit, we will just report it as 'no data'. The sample from the confirmed visit will not be tested for resistance.
 2. No. and percentage of subjects with IN resistance mutations or major mutations in the classes of NNRTI, NRTI, PI, respectively
 3. Separate outputs by phenotypic cut-off and by number of drugs to which subjects are resistant.

Additional analyses for HIV-1 resistance may be carried out on peripheral blood mononuclear cell (PBMC) samples collected at Baseline for CVF subjects.

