To assess viral resistance in participants experiencing confirmed virologic failure (CVF)	
 Incidence of treatment emergent genotypic and phenotypic resistance to CAB, RPV and other on-study ART through Week 48
To assess the impact of Baseline third agent treatment class (INI, NNRTI, or PI) on efficacy, safety, tolerability, and viral resistance of CAB LA + RPV LA compared to continuation of current ART	
By Baseline third agent treatment class:
 
 Proportion of participants with a 'virologic failure' endpoint as per FDA Snapshot algorithm at Week 48 (Intent-to-Treat Exposed [ITT-E] population). Proportion of participants with Plasma HIV-1 RNA <50 c/mL at Week 48 using the FDA Snapshot algorithm (Intent-to-Treat Exposed [ITT-E] population) Incidence and severity of select AEs and laboratory abnormalities over time including Week 48 Proportion of participants who discontinue treatment due to AEs over time including Week 48 Absolute values and changes in select laboratory parameters over time including Week 48 Incidence of observed genotypic and phenotypic resistance to current antiretroviral regimen and to CAB or RPV for participants meeting confirmed virologic failure (CVF)
To characterize CAB and RPV concentrations and population pharmacokinetics and identify important determinants of variability.	
 Plasma PK parameters for CAB LA and RPV LA (when evaluable, C_{trough}, concentrations post dose [$\sim C_{max}$], and area under the curve [AUC]) Demographic parameters including, but not limited to, age, sex, race, body weight, body mass index, and relevant laboratory parameters will be evaluated as potential predictors of inter- and intra-participant variability for pharmacokinetic parameters

To evaluate the antiviral and immunologic effects, safety, tolerability, and viral resistance of CAB LA + RPV LA for participants during the Extension Phase
 
 For participants randomized to CAB LA+ RPV LA at Day 1 For participants electing to 	
 Proportion of participants with plasma HIV-1 RNA < 50 c/mL over time including Week 96 (observed case) Proportion of participants with confirmed virologic failure (two consecutive plasma HIV-1 RNA levels ≥ 200 c/mL after prior suppression to <200 c/mL)

Objectives	Endpoints

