2.3. Study Design

Overview of Study Design and Key Features	

The diagram illustrates the study design timeline. It is divided into three main phases: Screening Phase, Maintenance Phase, and Extension Phase. The Screening Phase (Day 1) involves randomization (1:1, N=570) into two arms: 'PI, NNRTI or INI Based Regimen with 2 NRTI Backbone' and 'Oral CAB + RPV'. The Maintenance Phase (Day 1 to Week 52) continues with 'PI, NNRTI or INI Current ART' for the first arm and 'CAB LA + RPV LA' for the second. At Week 52, the first arm has an optional 'Extension Phase' (Oral CAB + RPV), while the second arm enters an 'Extension Phase'. Both arms have a '1° Endpoint' at Week 48 and a '2° Endpoint' at Week 96. 'Q4 Weeks' intervals are marked between Week 48 and Week 52, and between Week 56 and Week 96.
	

N=570, randomized 1:1 to each arm and stratified by baseline 3rd Agent class and sex at birth. # Must be on uninterrupted current regimen (either the initial or second cART regimen) for at least 6 months prior to Screening. Documented evidence of at least two plasma HIV-1 RNA measurements <50 c/mL in the 12 months prior to Screening: one within the 6 to 12 month window, and one within 6 months prior to Screening. No history of virologic failure. No evidence of viral resistance based on the presence of any resistance-associated major INI, or NNRTI mutation (except K103N) from prior genotype assay results. No current or prior history of etravirine use. ΨINI based regimen excludes abacavir/dolutegravir/lamivudine (TRIUMEQ), and INI therapy will be capped at approximately 40% of study enrolment for current ART †Optional Extension Phase to CAB LA + RPV LA at Wk 52 for participants randomized to current ART ‡Participants who withdraw from IM arm must go into 52 week long term follow up phase
	

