13.6.7. Viral Genotype and Phenotype

Genotype (Plasma sample at time of CVF and PBMC at Baseline)

Amino Acid Changes

- A mutation is considered present whenever the encoded amino acid residue differs from the amino acid that would have been encoded by the wild-type (e.g., HXB2, NL43) comparator gene; e.g., Q148K.
- If the encoded amino acid is seen as a mixture of wild-type and mutant amino acid, e.g., Q148Q/K, the mutated amino acid is considered present at the codon of interest.
- If the encoded amino acid is seen as a mixture of two or more amino acids, which may or may not include wild type, e.g., Q184K/H or Q184K/H/Q, etc., for the purposes of calculating the number of mutated amino acids, only one mutation is considered to be present at the codon of interest.

Representation of Amino Acid Changes

Mutations	Amino acid change
T69S	Single mutation from amino acid 'T' (vendor reference) to 'S' (sample) at codon '69'
Q148H/K/R	Mixture of amino acid mutations 'H', 'K' and 'R' (sample) from amino acid 'Q' (vendor reference) at codon '148'
_69_1T	First insertion of amino acid 'T' (sample) at codon '69'
_69_2S	Second insertion of amino acid 'S' (sample) at codon '69'
_69_3S/A	Third insertion of a mixture of amino acids 'S' and 'A' (sample) at codon '69'
L74L/-	Mixture of amino acid 'L' (sample) and a deletion at codon '74'
V75-	Single deletion of amino acid (sample) at codon '75'

Resistance Associated Mutations

- Known INI mutations associated with the development of resistance to RAL, EVG or DTG:

Amino Acids in HIV Integrase for Analysis	H51Y, T66A/I/K , E92Q/V/G , Q95K, T97A, G118R, F121Y , E138A/K/T, G140A/C/R/S**, Y143C/H/R/K/S/G/A , P145S , Q146P , S147G , Q148H/K/R/N , V151I/L/A , S153F/Y, N155H/S/T , E157Q, G163R/K, S230R, R263K, L68V/I*, L74I*, E138D*, V151I*, G193E*
---	--

NOTES:

- Draft listing; may be modified in case of additional substantive data availability.
- INI mutations listed taken from Stanford HIV Resistance Database (http://hivdb.stanford.edu/DR/cgi-bin/rules_scores_hivdb.cgi?class=INI cited 03Feb2017) and accessed on 07Mar 2017.
- Each INI mutation listed had a score of ≥ 15 . INI substitutions listed above in bold had a score of =60.
 - * Denotes additional INI mutations added as they were identified during in vitro passage of DTG or seen in a previous DTG study in INI-experienced subjects (ING112574).
 - **G140R is potentially associated with CAB based on in-stream data monitoring of CVF subjects

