Darunavir/r	DRV/r	PI	(10 – 90) ^a
Ritonavir	RTV	PI	2.5
Enfuvirtide	T20	FI	6.48
Cabotegravir	CAB	INI	2.5
Raltegravir	RAL	INI	1.5
Elvitegravir	EVG	INI	2.5
Dolutegravir	DTG	INI	(4-13) ^a

a. clinical cutoff (lower cutoff – higher cutoff).

Phenotypic susceptibility to each drug in a subject’s background regimen is determined by applying drug-associated cutoffs as defined by the PhenoSense algorithm to the phenotypic fold resistance as below:

Full Sensitivity

Fold Change	Interpretation
> clinical lower cutoff or biologic cutoff	resistance
≤ clinical lower cutoff or biologic cutoff	sensitive

Partial Sensitivity

Fold Change	Interpretation
> clinical higher cutoff	resistance
≤ clinical higher cutoff and > clinical lower cutoff	partially sensitive
≤ clinical lower cutoff	sensitive

PHENOTYP dataset from Monogram contains the phenotypic susceptibility for each drug derived from the cutoff listed above. Thus, phenotypic susceptibility (i.e. full sensitivity and partial sensitivity) will not be re-derived for our analysis.

Genotypic and Net Assessment Susceptibility

Genotypic and Net assessment susceptibility to all licensed antiretroviral drugs and CAB will be determined from Monogram Inc. and will be reported with the categories of ‘resistance’, ‘partially sensitive’, and ‘sensitive’ as what will be performed for phenotypic susceptibility. Genotypic and Net assessment susceptibility will be assessed at time of CVF using plasma sample, Genotypic susceptibility will be assessed at baseline using PBMC.

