13.13.15. Virology Tables

For Week 96/EOS IA, each display will be split into two Tables, one for Maintenance+Extension phases for Q4W arm only, and one for Extension phase for Current ART arm only)					
No.	Population	IDSL / TST ID / Example Shell (mock up below from study 200056\wk48idsl)	Title	Programming Notes	Deliverable
Genotype					
8.1	CVF	Table 9.1001	Summary of the Prevalence of Known INI Resistance Mutations at time of CVF (Maintenance phase) – Plasma Sample	(identify known INI resistance mutation per Section 13.6.6). need to add small 'n' for actual no. of subjects included in the analysis. The % will be based on 'n' rather than 'N'	WK48
8.2	CVF	Table 9.1003 (modify region to class)	Summary of the Prevalence of Major Resistance Mutations of NRTI, NNRTI and PI Class at time of CVF(Maintenance phase) - Plasma Sample	(identify Major Mutation of NRTI, NNRTI, PI class per Section 13.6.6). need to add small 'n' for actual no. of subjects included in the analysis. The % will be based on 'n' rather than 'N' (programming for defining class: can refer to arenv/arprod/gsk1349572/mid200304/week24/drivers/t_adpf_4001.sas	WK48
Phenotype					
8.3	CVF	Table 9.1005	Summary of Phenotype Susceptibility at time of CVF (Maintenance phase) - - Plasma Sample		WK48
8.4	CVF	Table 9.1005	Summary of Genotypic Susceptibility at time of CVF (Maintenance phase) - - Plasma Sample		WK48
8.5	CVF	Table 9.1005	Summary of Net Assessment at time of CVF (Maintenance phase) - Plasma Sample		WK48

CONFIDENTIAL

201585

For Week 96/EOS IA, each display will be split into two Tables, one for Maintenance+Extension phases for Q4W arm only, and one for Extension phase for Current ART arm only)					
No.	Population	IDSL / TST ID / Example Shell (mock up below from study 200056\wk48id sl)	Title	Programming Notes	Deliverable
8.6	CVF	Table 9.1006	Summary of Phenotype: Number of Drugs to Which Subject are Resistant at time of CVF(Maintenance phase) - Plasma Sample		WK48
8.7	CVF	Table 9.1007	Summary of Phenotypic Susceptibility to CAB and RPV at time of CVF(Maintenance phase) - Plasma Sample		WK48
8.8	CVF	Shell TV1	Summary of Viral load, Genotypic and Phenotypic data for Subjects Who Met Confirmed Virologic Failure Criteria During the Maintenance Phase		HL, WK48
8.9	CVF	Shell TV1	Summary of Viral load, Genotypic and Phenotypic data for Subjects who Met Confirmed Virologic Failure Criteria During the Extension Phase		WK48, 96, EOS

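### The resistance endpoint is treatment-emergent, but the planned displays report resistance present at failure with no baseline condition

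*SAP*

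**What the plan says.** **Endpoint.** Section 2.2 lists, under the objective on viral resistance in participants with CVF, the "Incidence of treatment emergent genotypic and phenotypic resistance to CAB, RPV and other on-study ART through Week 48". The Extension Phase objective repeats it through Week 96. A separate endpoint, by baseline third-agent class, asks for observed resistance at CVF.

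**Definition of a mutation.** Section 13.6.7: "A mutation is considered present whenever the encoded amino acid residue differs from the amino acid that would have been encoded by the wild-type" comparator gene. Phenotype is likewise a fold change against a wild-type control virus.

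**What is counted.** Table 8 in Section 11 has two genotype rows, one for prevalence and one for on-treatment mutations. Both carry footnote 2: "No. and percentage of subjects with IN resistance mutations or major mutations in the classes of NNRTI, NRTI, PI, respectively". Section 13.13.15 titles display 8.2 "Summary of the Prevalence of Major Resistance Mutations of NRTI, NNRTI and PI Class at time of CVF", and display 8.1 has the matching title for INI mutations. Displays 8.3 to 8.7 give phenotypic, genotypic and net susceptibility at CVF.

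**Baseline samples.** Section 11: "Additional analyses for HIV-1 resistance may be carried out on peripheral blood mononuclear cell (PBMC) samples collected at Baseline for CVF subjects". Section 13.6.7: "Genotypic susceptibility will be assessed at baseline using PBMC". Footnote q of the schedule in Section 13.2.1 has PBMCs collected at Day 1.

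**Entry.** The design summary in Section 2.3 requires no evidence of any "resistance-associated major INI, or NNRTI mutation (except K103N) from prior genotype assay results".

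**The concern.** Emergence is a change: a mutation seen at failure that was not there before treatment. Both the mutation definition and the Table 8 count compare the failure sample with a laboratory reference and never with the participant's own earlier virus. The displays therefore describe how much resistance is present among failures, which is a different quantity from the one Section 2.2 names.

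The participants here are treatment-experienced and switching from a suppressive regimen, so virus carrying older mutations is a realistic possibility, and the SAP itself allows for one such mutation at entry. At stake is how the few failures in each arm are described: selected on the randomised regimen, or carried in from before. If the baseline assay is optional and the comparison rule unwritten, that reading is left until after the failures have been seen, in an open-label trial.

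**Working it through.** The SAP gives no figure to reproduce, so the check sets its sections side by side and then follows one participant through the stated rules.

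| Element | Treatment-emergent endpoint (2.2) | Planned displays |
|---|---|---|
| Reference for a mutation | the participant's virus before treatment (implied by emergent) | wild-type gene (13.6.7) |
| Reference for phenotype | the participant's virus before treatment (implied) | wild-type control virus (13.6.7) |
| Count | newly resistant | any listed mutation at CVF (Table 8, footnote 2) |
| Baseline sample | needed for every failure | optional in Section 11, planned in 13.6.7, genotypic only |
| Display of baseline against failure | needed | none named in the titles of 8.1 to 8.10 |

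**One participant traced.**

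1. K103N is known from a prior genotype. Section 2.3 permits entry.
2. The participant meets CVF. Under Table 8 footnote 1, the plasma sample from the suspected-failure visit is tested. Suppose it shows K103N and no other listed mutation.
3. Under 13.6.7, K103N differs from wild type, so it is present. It is also on the major NNRTI list in that section.
4. Footnote 2 counts the participant, who adds 1 to the NNRTI row of display 8.2.
5. Under a treatment-emergent rule the same participant adds 0.

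**Size.** The programming notes for 8.1 and 8.2 take percentages over n, the participants with data. If k of them carry only pre-existing mutations of a class, the class percentage exceeds the emergent percentage by k/n. The SAP does not give n, so the values below are assumptions, with k = 1:

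- n = 3: 1/3 = 33 points
- n = 5: 1/5 = 20 points
- n = 10: 1/10 = 10 points

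Against a whole randomised arm of 570/2 = 285, the same case is 1/285 = 0.35 points.

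**Beyond K103N.** The entry criterion as summarised in Section 2.3 does not name NRTI or PI mutations, yet display 8.2 counts them. It also rests on prior genotype results. These are further routes by which a mutation already present could be counted, but the SAP gives nothing from which to size them.

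**The case against.** Five points can be made for the plan.

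- *Baseline genotyping is planned.* A reader of Section 11 alone might infer that it is merely optional. The SAP does not support that reading, because 13.6.7 states that it will be done and its headings name the baseline PBMC sample. What stands is that the two sections conflict and that neither gives a comparison rule.
- *The prevalence tables are honest about what they are.* A reader might infer that the plan reports pre-existing mutations as treatment-emergent outcomes. It does not: 8.1 and 8.2 are labelled as prevalence at CVF, and they suit the observed-resistance endpoint by third-agent class. The defect is the absence of an emergent display, not the presence of these two.
- *Table 8 has an on-treatment-mutation row.* This suggests that something beyond prevalence was meant. But the row is undefined, shares the prevalence footnote, and has no separately titled display in Section 13.13.15.
- *Displays 8.8 to 8.10 may show baseline data by participant.* They might; their shell is in a separate document. With few failures, emergence could be read there by eye. That would still leave no derivation rule, and the counts in 8.1 and 8.2 would be unchanged.
- *The size is illustrative.* This is correct. It concerns one class row and assumed values of n. Nothing in the SAP shows that a K103N would change the CAB and RPV phenotypic results in display 8.7.

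**Conclusion.** The point holds in a limited form. The SAP states a treatment-emergent endpoint, and its counting rule and displays 8.1 to 8.7 estimate prevalence at failure instead. K103N shows, from the SAP's own entry criterion and mutation list, that the two can differ. Each pre-existing case adds 1/n to a class percentage, with n unknown.

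It should not be read as saying that resistance will be overstated. That depends on whether any failure carries an older mutation, which the SAP cannot tell us, and on how the results are worded. No test, margin or multiplicity step in Section 5.5 uses these displays; they are descriptive, and the primary and key secondary comparisons are unaffected. It is still worth correcting before the Week 48 analysis, because a named secondary endpoint has no defined derivation.

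**What to change.** 1. Reconcile Section 11 with Section 13.6.7 so that baseline PBMC genotyping is done for every CVF participant who has a sample.
2. In 13.6.7, define treatment-emergent genotypic resistance as a listed mutation in the suspected-failure plasma sample that is absent from the Day 1 PBMC genotype. Show participants without a baseline result separately as baseline unknown. Use the same definition for the on-treatment-mutation row of Table 8.
3. Add a treatment-emergent column or display. Keep 8.1 and 8.2 as prevalence tables for the observed-resistance endpoint.
4. The baseline PBMC assessment is genotypic only, so there is no baseline phenotype to compare with. Either label the phenotypic results in 8.3, 8.6 and 8.7 as resistance at failure, or state how phenotypic emergence is judged, for example by reading them together with the emergent genotype.

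The cost is SAP wording, one column or display, and an assay that 13.6.7 already plans on samples already scheduled, for CVF participants only.

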13. APPENDICES

Section	Appendix
RAP Section 4 : Analysis Populations	
Section 13.1	Appendix 1 : Protocol Deviation Management and Definitions for Per Protocol Population
RAP Section 5 : General Considerations for Data Analyses & Data Handling Conventions	
Section 13.2	Appendix 2 : Schedule of Activities
Section 13.3	Appendix 3 : Assessment Windows
Section 13.4	Appendix 4 : Study Phases and Treatment State
Section 13.5	Appendix 5 : Data Display Standards & Handling Conventions
Section 13.6	Appendix 6 : Derived and Transformed Data
Section 13.7	Appendix 7 : Reporting Standards for Missing Data
Section 13.8	Appendix 8 : Values of Potential Clinical Importance
Section 13.9	Appendix 9 : Population Pharmacokinetic (PopPK) Analyses
Section 13.10	Appendix 10 : Pharmacokinetic / Pharmacodynamic Analyses
Section 13.11	Appendix 11 : Snapshot Algorithm Details
Section 13.14	Appendix 14 : IDMC
Other RAP Appendices	
Section 13.12	Appendix 12 : Abbreviations & Trade Marks
Section 13.13	Appendix 13 : List of Data Displays
Separate document	Example Mock Shells for Data Displays

13.1. Appendix 1: Protocol Deviation Management and Definitions for Per Protocol Population

13.1.1. Exclusions from Per Protocol Population

Important protocol deviations leading to exclusion from Per Protocol population are those deviations which may

- i. directly impact the efficacy endpoint of HIV-1 RNA; or
- ii. lead to permanent discontinuation of IP/withdrawal and hence indirectly impact the efficacy endpoint by causing data to be missing.

The following criteria define the protocol deviations which, if they occur prior to an analysis timepoint of interest (e.g. Week 48/96), will lead to exclusion of a subject from the Per-Protocol population for that analysis. Potential protocol deviations leading to exclusion from PP population will be reviewed by the study team to confirm that they meet these criteria. A final review will occur before the clinical database has been frozen for analysis.

A subject meeting any of the following criteria will be excluded from the Per Protocol population based on case-by-case clinical determination:

Number	Exclusion Description
01	Subject deviates from inclusion or exclusion criteria that may significantly affect exposure, response to therapy or subject safety or that are fundamentally inconsistent with the intended study population, as recorded in the Protocol Deviation form in the eCRF based on study team review (where indicated in the PDMP as case-by-case determination).
02	
Subject has non-compliance with IP (including IM dosing errors) or took/received incorrect IP (i.e., other than the one to which they were randomized) that is:
 
Maintenance phase
 
 1. > 10% of total time on-treatment with under dosing deviations up to the analysis timepoint of interest (e.g. Week 48). 2. Two or more injection intervals affected by over dosage deviations (e.g. extra injection or excessive volume administered, length of time between injections less than 3 weeks, excluding split doses) up to the analysis timepoint of interest. 
For this purpose, the total number of non-compliant under dosing days up to the analysis timepoint of interest, is derived as follows:
 
 • Control Arm: 
 a. Interruptions of control arm ART for reasons other than treatment-related adverse events/laboratory abnormalities (based on concomitant ART eCRF forms); • Q4W IM Arm: 
 a. Length of time until next injection from date of dosage/administration deviation potentially resulting in under dosage (e.g. 1ml administered instead of 2ml) b. Length of time between injections exceeding 5 weeks (e.g. missed or late

Number	Exclusion Description
	
injection visit) for post Week 12 and exceeding 4 weeks for Week 8 and Week 12
 
c. Interruptions of oral lead-in or oral bridging (if necessary) for reasons other than treatment-related adverse events/laboratory abnormalities (based on eCRF Exposure forms);
 
Note: The total no. of under dosage non-compliance days will be derived based on the above rules and censored at the date of last on-treatment viral load for the visit of Week 48 snapshot analysis during Maintenance phase.

03	
Prohibited medications: receiving ART medication other than that prescribed/allowed by the study (excluding permanent changes in ART regimen; such cases will be retained as 'HIV1-RNA≥50 c/mL' in the per protocol snapshot analysis) or receiving prohibited concomitant medication that would impact exposure or response to therapy with duration and route of administration taken into consideration, as recorded in the Protocol Deviation form in the eCRF based on study team review (where indicated in the PDMP as case-by-case determination)

04	
Permanent discontinuation of IP/withdrawal due to a reason of "Protocol Deviation" (as recorded in the eCRF Conclusion form).

05	
Other important protocol deviations that exclude subject from Per protocol population as recorded in the Protocol Deviation form in the eCRF based on study team review (where indicated in the PDMP as case-by-case determination).

Non-compliance Rate (under dosage deviation)

The rate of under dosage non-compliance for each subject will be derived based on the total number of days impacted by under dosage deviations up to analysis timepoint of interest (e.g. for Week 48 analysis, the analysis timepoint of interest is the date of Last on-treatment viral load for the visit of Week 48 Snapshot analysis), against the total no. of intended exposure days up to the same timepoint, see the example below for Week 48 analysis.

Total no. of intended exposure days = Date of Last on-treatment viral load* - Date of treatment start at Maintenance phase +1

*last on-treatment viral load is the viral load used for snapshot analysis at week 48.

Non-compliance (under dosing) rate= total no. of under dosage non-compliance days /total no. of intended exposure days * 100

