13.11. Appendix 11: Snapshot Algorithm Details

Detailed Algorithm Steps

- Consider an analysis visit window for Week X (e.g. Week4, ...Week 24, Week 48 et al). The Window for Week 24/48 visit is defined in Table 11 (e.g. window for Week 48 is ± 6 Week: $295 \leq \text{Study Day} \leq 378$) and in Table 9 for other visits through to Nominal Week 52 at Maintenance Phase. The Snapshot Analysis at post Maintenance Phase will not be appropriate because a large portion of responders will be switched to other studies and not all subjects would have the chance to reach same timepoint.
- The HIV1-RNA threshold of 50, 200 copies/mL will be analysed, respectively, in this study
- The analysis window 'Week 48' and HIV1-RNA threshold of '50 copies/mL' are used for the purpose of illustration. A subject's Snapshot response and reason at Week 48 are categorized as below.
 - HIV1-RNA < 50 copies/mL
 - HIV1-RNA ≥ 50 copies/mL
 - Data in window not below 50
 - Discontinued for lack of efficacy
 - Discontinued for other reason while not below 50
 - Change in background therapy*
 - No Virologic Data at Week 48 Window
 - Discontinued study due to AE or death
 - Discontinued study for other reasons
 - On study but missing data in window

* Note: since changes in ART are not permitted in this protocol, all such subjects who change ART during the maintenance phase will be considered 'HIV1-RNA ≥ 50 copies/mL'. if the change in ART is made prior to an analysis timepoint. Subjects with protocol permitted oral bridging treatment will not be considered ' HIV1-RNA ≥ 50 copies/mL' due to 'change in ART'.

- The steps in determining response and reasons are indicated in Table below, in the order stated.

Detailed steps		
Please note that the following scenarios will NOT be penalized Per Snapshot algorithm (i.e. please excluding these scenarios from Condition 1-4).		

 • Dose reduction, dropping a component, or change in formulation (e.g. 'Tivicay + Kivexa' to 'Triumeq' with the identical ingredients) 		
Condition ('Week 48' indicates Week 48 window)	Response	Reasons
1. If non-permitted change in background therapy prior to Week 48	HIV1-RNA ≥ 50	Change in background therapy
2.If permitted change ^[a] in background therapy prior to Week 48 AND the latest on-treatment VL prior to/on the date of change is ≥ 50 c/m (NA to this study)	HIV1-RNA ≥ 50	Change in background therapy

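### The Per-Protocol under-dosing rule has no exception for injection gaps covered by permitted oral bridging and does not fix which days of a gap count, so it can exclude fully dosed CAB-arm participants

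*SAP*

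**What the plan says.** SAP Section 13.1.1, criterion 02, makes under-dosing a ground for exclusion from the Per-Protocol population when it reaches "> 10% of total time on-treatment with under dosing deviations up to the analysis timepoint of interest". The days are built up by arm.

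- **Control arm, item a:** "Interruptions of control arm ART for reasons other than treatment-related adverse events/laboratory abnormalities".
- **Q4W IM arm, item a:** after a deviation such as a reduced volume, the time from that deviation to the next injection.
- **Q4W IM arm, item b:** "Length of time between injections exceeding 5 weeks (e.g. missed or late", continuing "injection visit) for post Week 12 and exceeding 4 weeks for Week 8 and Week 12".
- **Q4W IM arm, item c:** "Interruptions of oral lead-in or oral bridging (if necessary) for reasons other than treatment-related adverse events/laboratory abnormalities".

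The non-compliance rate at the end of the same section takes as numerator the "total number of days impacted by under dosage deviations up to analysis timepoint of interest". The denominator is given as "Total no. of intended exposure days = Date of Last on-treatment viral load", minus the Maintenance treatment start date, plus 1.

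Two other places deal with oral bridging. Appendix 11 (Section 13.11) says "Subjects with protocol permitted oral bridging treatment will not be considered" as having HIV-1 RNA at or above 50 c/mL on the ground of a change in ART. The adherence categories in Section 13.6.2 list missed injections with bridging separately from those without.

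**The concern.** Item b carries no bridging exception. Item c penalises a participant only when bridging is interrupted, which implies that uninterrupted bridging is compliant dosing; yet item b, read as written, adds the same days to the under-dosing count. A participant who missed injections but took oral CAB + RPV throughout, as the protocol permits, can therefore pass the 10% threshold without one uncovered day.

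The count itself is also open. Item b can mean the full interval between two injections, in parallel with item a of the same arm, or only the days beyond the limit. Nothing says how days that fall under more than one item are handled.

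A smaller point is that the control-arm rule and item c exempt interruptions for treatment-related adverse events or laboratory abnormalities, and item b does not.

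At stake is the Per-Protocol analysis, the only one listed under sensitivity and supportive analyses for both the primary endpoint (Section 7.1.5.1) and the key secondary endpoint (Section 7.2.5.1). It is meant to show the effect of important deviations, so what counts as a deviation should be fixed before the data are frozen, particularly in an open-label trial.

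**Working it through.** **Inputs**

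- Threshold: more than 10% (Section 13.1.1).
- Week 48 target day: the formula in Section 13.3.1 gives 7 × 48 + 1 = 337, which agrees with Table 9. The Week 48 Snapshot window is Day 295 to 378 (Table 11), and the denominator can lie anywhere in it.
- Planned interval: 28 days (Section 13.6.4). One missed injection gives a 56-day gap, two consecutive ones an 84-day gap.
- Limits in item b: 35 days after Week 12; 28 days for Weeks 8 and 12.

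The SAP gives no worked under-dosing rate, so 337 is the only stated figure to reproduce.

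**Days needed to exclude**

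0.10 × 337 = 33.7, so 34 days or more. At Day 295: 29.5, so 30. At Day 378: 37.8, so 38.

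**Rate = counted days / intended exposure days, after Week 12**

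| Gap | Excess over 35 days, Day 337 (range over window) | Whole interval, Day 337 (range over window) |
|---|---|---|
| 36 days | 1/337 = 0.3% (0.3%) | 36/337 = 10.7% (9.5–12.2%) |
| 56 days | 21/337 = 6.2% (5.6–7.1%) | 56/337 = 16.6% (14.8–19.0%) |
| 84 days | 49/337 = 14.5% (13.0–16.6%) | 84/337 = 24.9% (22.2–28.5%) |

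- **84 days:** above 10% under both readings and across the whole window, even if every day beyond the limit was covered by oral drug.
- **56 days:** always kept if excess days count, always above the threshold if the interval counts.
- **36 days:** the contrast holds at Day 337 but not throughout, since 36/378 = 9.5% is kept.
- On excess days, the smallest single gap that excludes at Day 337 is 35 + 34 = 69 days (65 at Day 295, 73 at Day 378).

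**Under the 28-day limit at Weeks 8 and 12**

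A missed Week 8 injection (56-day gap) gives 28/337 = 8.3% on excess days (7.4–9.5%), kept. Two 29-day intervals give 2/337 = 0.6% on excess days but 58/337 = 17.2% on whole intervals.

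**The adverse-event exemption**

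A 56-day interruption of control ART for a treatment-related adverse event scores 0 days. A 56-day injection gap after Week 12 for the same reason scores 21 days (excess) or 56 days (whole interval).

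**Scale in the Per-Protocol comparison, by assumption only**

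The SAP does not say how many participants will be bridged. Suppose 570/2 = 285 per arm, with 6, 9 or 11 failures in each arm, and 28 CAB-arm participants without failure removed (285 − 28 = 257). The unadjusted upper 95% limit then moves from 2.36% to 2.72%, from 2.87% to 3.37%, or from 3.16% to 3.76%, against a 6% margin. Removing participants who did fail would lower the CAB rate instead. This is an illustration, not an estimate.

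**The case against.** The case against is substantial, and much of it stands.

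- **Review.** Exclusion is by case-by-case clinical determination after the study team has checked the criteria. Criterion 02 opens with non-compliance with study drug, and item c names bridging and counts only its interruptions. A sensible team could decide that a bridged gap is not a deviation. A reader might infer that the rule will remove compliant participants; the document supports only that it can. Review does not cure the wording, though: the team confirms whether the criteria are met, and a bridged gap meets item b as written.
- **Reading.** Excess days are the more natural reading. Item a in the same arm speaks of time until the next injection, while item b speaks of time beyond a limit. The whole-interval reading would also score a 36-day gap at 10.7% but a half-volume injection at 28/337 = 8.3%. So it should not be inferred that one bridged missed injection leads to exclusion. The 84-day case does not depend on this choice.
- **Arms.** A reader might infer that adverse-event gaps are exempt in one arm only. They are not: item c exempts such interruptions of oral dosing in the CAB arm. After Week 12, item b also allows a week beyond the 28-day schedule, and the control rule has no such allowance. Leaving item b without the exemption is defensible, because an uncovered gap may affect HIV-1 RNA whatever its cause.
- **Supporting text.** The Appendix 11 sentence concerns only the change-in-ART category, and the adherence categories are descriptive. They show that the SAP treats bridging as a distinct, permitted state; they do not define compliance for the Per-Protocol population.

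**Conclusion.** The point holds as a contradiction within criterion 02, of moderate weight. Item b scores covered days as under-dosing while item c implies that they are compliant, and two consecutive bridged injections exceed 10% whichever way the days are counted. For one bridged injection the unsettled count decides the outcome. The figures assume 28-day scheduling, gaps falling after Week 12 and complete before the Week 48 viral load, and full oral cover.

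The consequence is confined to the Per-Protocol sensitivity analysis. Non-inferiority is declared on ITT-E (Sections 5.5.1 and 5.5.2) and is not affected. Because the number of bridged participants is not given, the effect on the Per-Protocol estimate cannot be sized. The document therefore does not support the inference that agreement between the two analyses would be uninformative. The missing adverse-event exemption is an inconsistency to be explained or removed, not a demonstrated bias against either arm.

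**What to change.** Before database freeze, restate item b so that it counts only days beyond the SAP's own limits (35 days, or 28 days for Weeks 8 and 12) that are not covered by oral CAB + RPV bridging. State that days falling under more than one of items a, b and c count once. Keep the 10% threshold. A fully bridged gap then scores 0 days, and an unbridged 84-day gap still scores 49/337 = 14.5%.

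Separately, reconcile the treatment-related adverse-event and laboratory exemption between the control-arm rule, item c and item b: either align it or state why injection delays are treated differently. Check first that a reason is recorded for each late injection. The summary of protocol Amendment 3 in SAP Section 1 mentions removing a requirement to record treatment delays, while note 2 to Table 5 expects reasons for dose interruption in the exposure listing.

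The cost is a wording change and a revised derivation. Injection and oral dosing dates already feed the planned exposure derivations (Section 13.6.2). The downside is that slightly more CAB-arm participants stay in the Per-Protocol set. None of this changes a dosing rule.
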